6.11.3. Secondary Efficacy Analyses

6.11.3.1. The Primary Analyses for Secondary Efficacy Endpoints

The ITT population by censoring the post-rescue data is the analysis population for secondary efficacy endpoints. Data for secondary endpoints will be summarized as described in Section 6.1. The MMRM described in Section 6.1 will be used to analyze each secondary

continuous efficacy endpoint: change from baseline in FSG and body weight. The result will be reported as detailed in Section 6.11.1.

The proportion of patients achieving HbA1c target <7.0% will be analyzed using repeated measures logistic regression mixed model described in Section 6.1 as the primary analysis. Pooled country, treatment, visit, treatment-by-visit interaction will be fitted as fixed effects, baseline HbA1c as a covariate. This model will be fitted to leverage all available data without imputation.

6.11.3.2. Supporting Analyses For Secondary Efficacy Endpoints

As a sensitivity analysis for proportion of patients on HbA1c targets, a logistic regression model will be fitted with pooled country and treatment as fixed effect, baseline HbA1c as a covariate to analyze the endpoint data. Prior to this analysis, the missing data or the patients rescued up to Week 18 will be imputed as not achieving HbA1c target.

The analyses listed in Section 6.11.3.1 will be repeated for the ITT population without censoring the post rescue data as a sensitivity analysis to FSG and body weight change from baseline.

6.11.3.3. Bayesian Analyses For Exploratory Objectives

A similar Bayesian ITP model listed in Section 6.11.2.3 will be fitted to analyze body weight change from baseline as a supportive analysis by only changing the prior information with Θ_i , $\alpha \sim N(0, 100)$.

Probabilities based on posterior distributions of the parameter of interest: change from baseline in body weight at Week 18, and Week 26 will be generated from this model using 10000 MCMC samples with thin=10 and burn-in=10000:

$$\text{pr}(\Delta_i - \Delta_{\text{dula1.5mg}} < \text{threshold})$$

i stands for dulaglutide 3.0 mg or 4.5 mg.

The threshold for this analysis will be -1 kg and -2 kg.

If this model doesn't converge, the similar alternative Bayesian model in Section 6.11.2.3 will be adopted with the priors: $\alpha, \beta[i,t] \sim N(0, 100)$.

The probability for Week 26 will be assumed to be the same as Week 18 from this model.

The imputed data along with non-missing 18-week data will be analyzed using an ANCOVA model following the same method listed in Section 6.11.2.2.

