## 5.5. Justification for Doses

The rationale for dulaglutide dose selection in this study was based on PK/pharmacodynamic (PD) model projections centered on identifying 1 or more doses higher than 1.5 mg that may yield up to or greater than 0.2% additional HbA1c reduction and up to or greater than 1.0 kg additional weight loss at the Week 18 endpoint, with an acceptable safety and tolerability profile compared to placebo and the 1.5 mg dose. The chosen higher dulaglutide doses (3.0 mg and 4.5 mg) were selected considering adequate separation in PK exposure range between the doses to enable evaluation of their efficacy and adverse effect profiles. Based on predicted plasma exposures in patients with T2D receiving the highest investigational dulaglutide dose of 4.5 mg, the margins of safety (ie, plasma exposure multiples at the no-observed-adverse-effect level [NOAEL]) in chronic toxicology studies in monkeys and rats were 162-fold and 55-fold, respectively.

The 2 titration algorithms for the investigational doses were designed based on PK/PD modeling, with the goal of alleviating GI AEs. The current predicted daily incidence of nausea and vomiting, together with observed data showing onset of such events diminishing by 4 to 6 weeks of treatment, suggest that utilizing a 4- to 6-week titration phase to reach the targeted dose will reduce the risk of new events with further uptitration by inducing tachyphylaxis. The titration algorithms will be initiated using 1 of the approved doses of dulaglutide (0.75 mg and 1.5 mg), because these doses do not require titration at initiation (see [Figure GBGJ.1](#) and also Section 5.4 for further details).

Study GBGJ is expected to inform the design of Phase 3 studies to further develop at least 1 higher dulaglutide dose by improving understanding of the effects of the 2 investigational dulaglutide doses on patient safety and tolerability, such as nausea and vomiting and the effect of an optimized dose-titration approach on these outcomes.

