6.11.2.3. Bayesian Analyses For Exploratory Objectives

A Bayesian integrated 2-component prediction (ITP) model (Fu and Manner 2010) will be fitted for the primary endpoint separately in ITT population by censoring all post rescue therapy data,

and in ITT population including all available data regardless of rescue medication or adherence to the study drug. Non-informative priors will be used in this model. In addition, the informative priors from the posterior for placebo and posterior for dulaglutide 1.5 mg obtained from Study H9X-MC-GBCF (GBCF) and Study H9X-MC-GBDE (GBDE) will be evaluated in this model to check the robustness of the analysis.

$$Y_{ijt} = (\theta_i + S_{ij} + \alpha \times (B_{ij} - \bar{B}) + \varepsilon_{ijt}) \times \left(\frac{1 - e^{k_i \times t}}{1 - e^{k_i \times 18}} \right)$$

Prior information: $\theta_i, \alpha \sim N(0, 3)$; $S_{ij}, \varepsilon_{ijt} \sim \text{uniform}(0.01, 3)$; $k_i \sim \text{uniform}(-1, 1)$ where Y_{ijt} represents HbA1c change from baseline from dose i , subject j at time t . Parameter θ_i is the predicted drug effect of dose i at 18-week therapy. The parameter S_{ij} is a random between-subject SD, and ε_{ijt} is the within subject SD. The B_{ij} is baseline HbA1c for subject j at dose i and \bar{B} is the overall arithmetic mean baseline HbA1c from all subjects. k_i is the parameter to represent how fast to reach the effect for dose i at Week 18.

Probabilities based on posterior distributions of the parameter of interest: change from baseline to Week 18, and Week 26 will be generated from this model using 10000 MCMC samples with thin=10 and burn-in=10000:

$$\text{pr}(\Delta_i - \Delta_{\text{dula1.5mg}} < \text{threshold})$$

i stands for dulaglutide 3.0 mg or 4.5 mg.

The threshold of -.15, -.2, and -.3% will be used, separately.

If this model fails to converge, an alternative Bayesian model will be fitted:

$$y_{ijt} \sim MVN(\mu[i, t], \Omega)$$

$$u[i, t] = \alpha \times (B[i, t] - \bar{B}_0) + \beta[i, t] \times T[i, t]$$

Where $\beta[i, t]$ is the effect for dose i at time t . Ω is the variance-covariance matrix.

The priors for each parameters are: $\alpha \sim N(0, 3)$, $\beta[i, t] \sim N(0, 3)$, $\Omega \sim \text{wishart}(t, t\text{-demension Identity matrix})$.

The probability for Week 26 will be assumed to be the same as Week 18 from this model.

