6.16. Interim Analyses and Assessment Committee

At least three safety interim analyses and one efficacy/safety interim analysis will be conducted according to the specifications included in the protocol. The purpose of the safety analyses will be to monitor the safety and tolerability of the 2 investigational dulaglutide doses. The interim efficacy/safety analysis will be conducted for internal clinical development planning purposes to enable preliminary dose-selection for Phase 3 planning. The study will not be stopped based on the efficacy results at this interim analysis.

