6.16.2.2. Evaluation Criteria

For safety only interim analyses, the totality of the safety data on AEs, SAEs, TEAEs, and AESIs, disposition, discontinuation due to AEs, ECG, vital signs, ADA, GI AEs, cardiovascular events, and safety laboratory analytes will be evaluated. The analysis for each mentioned parameter will be analyzed in the same way as defined in this SAP.

For efficacy/safety analysis, the AC will base their decision on the following criteria in addition to the safety parameters listed in the preceding paragraph:

HbA1c Criterion:

At least 80% probability that at least one dose of dulaglutide 3.0 or dulaglutide 4.5 mg reduces HbA1c by at least 0.2% compared to dulaglutide 1.5 mg at Week 18, that is,

$\Pr(\Delta_{\text{dula3.0 or dula4.5}} - \Delta_{\text{dula1.5}} < -0.2\%) \geq 80\%$]. The other thresholds of -0.15% and -0.3% will be also be evaluated. The probability will be at least 55% at the end of the study.

Other efficacy endpoint at week 18: change from baseline in body weight, will also be assessed relative to 1.5 mg as, $\Pr(\Delta_{\text{dula3.0 or dula4.5}} - \Delta_{\text{dula1.5}} < \text{threshold of } -1 \text{ and } -2 \text{ kg.}$

Safety Parameters:

Heart rate from ECG, pulse rate from vital signs using change from baseline to be assessed relative to placebo as, $\Pr(\Delta_{\text{dula3.0 or dula4.5}} - \Delta_{\text{placebo}} < \text{threshold of } 3, 5, 7, 10 \text{ bpm.}$

MMRM analysis results will be reported for change from baseline in HbA1c, body weight, selected ECG, vital signs, and pancreatic enzymes, too.

PK/PD exposure-response results will be generated based on a separate PK/PD analysis plan by PK/PD group.

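### The body-weight Bayesian model keeps the HbA1c SD priors, so both SDs are capped at 3 kg; if the between-subject SD is about 3.5 kg or more, the weight-loss probabilities versus 1.5 mg are too extreme

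*SAP*

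**What the plan says.** SAP 6.11.2.3 defines the ITP model for HbA1c change. Theta and alpha have N(0, 3) priors, S and epsilon have uniform(0.01, 3) priors, and the time-course parameter k has a uniform(-1, 1) prior. The text says that S "is a random between-subject SD, and" that epsilon is its within-subject counterpart. The equation uses the same symbols for the random terms themselves, so I read the uniform priors as priors on the SDs of those terms.

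SAP 6.11.3.3 applies a similar model to body-weight change "as a supportive analysis by only changing the prior information with" N(0, 100) for theta and alpha. It names no other change. The outputs are posterior probabilities that the difference from dulaglutide 1.5 mg lies below -1 kg or -2 kg. If the model does not converge, "the similar alternative Bayesian model in Section 6.11.2.3 will be adopted with the priors" N(0, 100) for its own mean parameters. That alternative is a multivariate normal model with no SD ceiling.

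The efficacy/safety interim (SAP 6.16.2.2) lists the same two weight thresholds: "change from baseline in body weight, will also be assessed relative to 1.5 mg as" the corresponding probabilities. SAP 6.16 gives the purpose of that interim as "to enable preliminary dose-selection for Phase 3 planning". Protocol 5.5 sets the scale of interest: doses projected to give "up to or greater than 1.0 kg additional weight loss at the Week 18 endpoint". The main analysis of weight is frequentist (SAP 6.11.3.1): "The MMRM described in Section 6.1 will be used to analyze each secondary" continuous efficacy endpoint, weight included.

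**The concern.** The priors on theta and alpha were widened for an outcome in kg, but the SD priors were not. For HbA1c the ceiling is harmless: 3 / 1.2 = 2.5 times the SD of 1.2% used for sample size. For weight there is no planning SD to set against 3 kg.

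If patients differ by more than the ceiling allows, the posterior for the between-subject SD piles up at 3. The dose difference then looks more precise than the data support, and its threshold probabilities move away from 50%. They are too high when the estimate is beyond the threshold and too low when it falls short.

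The planned fallback would not reliably catch this, because a chain pressed against a bound can converge normally. Protocol 5.4 chooses Bayesian methods for the comparison with 1.5 mg in order to guide Phase 3 dose selection, so these probabilities are outputs that people will read.

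**Working it through.** **Inputs from the documents.** About 60 completers per arm (SAP 5.2). About 120 completers at the interim (SAP 6.16.2.1), so 120 / 4 = 30 per arm under 1:1:1:1 allocation. Nine treatment-period weight measurements, Visits 4 to 12 (Protocol section 2). SD ceiling 3; thresholds -1 and -2 kg.

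**Assumptions.** Between-subject SD from 2.5 to 5 kg; within-subject SD 1 kg unless stated; complete visits; data that follow the ITP model.

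**The plan's own figure.** The only sizing statement concerns HbA1c. With 60 per arm, difference 1.0, SD 1.2 and two-sided 0.05, power is 99.5%, consistent with the stated 90% or more. Also 60 / 0.80 = 75 per arm and 300 / 0.70 = 429 screened. These figures agree with the plan but say nothing about weight.

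**Step 1: closed form.** The residual sits inside the bracket that the time factor multiplies. Dividing the outcome by that factor therefore leaves a random-intercept model, and for known k

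SE(difference) = sqrt{2 (S² + e²/9) / n}.

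At n = 60, S = 4, e = 1: sqrt{2 × (16 + 0.111) / 60} = 0.733 kg. With S held at 3: sqrt{2 × (9 + 0.111) / 60} = 0.551 kg. The ratio is 0.75.

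**Step 2: posterior with the prior bound.** An exact grid posterior over both SDs (four arms, k treated as known, expected sums of squares) compares an upper bound of 3 with one of 30. Entries are the posterior SD of the difference in kg, bound 3 / bound 30.

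| Between-subject SD | 60 per arm | Ratio | 30 per arm | Ratio |
|---|---|---|---|---|
| 2.5 kg | 0.463 / 0.463 | 1.00 | 0.659 / 0.660 | 1.00 |
| 3 kg | 0.533 / 0.555 | 0.96 | 0.743 / 0.790 | 0.94 |
| 3.5 kg | 0.546 / 0.646 | 0.85 | 0.765 / 0.920 | 0.83 |
| 4 kg | 0.548 / 0.738 | 0.74 | 0.772 / 1.050 | 0.74 |
| 5 kg | 0.550 / 0.921 | 0.60 | 0.776 / 1.311 | 0.59 |

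At a true SD of 4 kg the posterior mean of the between-subject SD is 2.99 with the bound at 3 and 4.02 with it at 30. The within-subject SD hardly matters: at 4 kg and 60 per arm the ratio runs only from 0.742 to 0.749 as it goes from 0.5 to 2 kg.

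**Step 3: full model.** MCMC of the whole ITP model with k sampled, on a few simulated data sets per setting, gave ratios of 0.96, 0.85, 0.75 and 0.62 at 3, 3.5, 4 and 5 kg (75 per arm). The within-subject SD stayed near 1, so it does not absorb the excess.

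**Step 4: reported probabilities.** Pr(difference < threshold) is close to Φ{(threshold − observed) / posterior SD}. For an observed -1.5 kg, threshold -1 kg and SD 4 kg: Φ(0.5 / 0.548) = Φ(0.91) = 82% with the bound at 3, and Φ(0.5 / 0.738) = Φ(0.68) = 75% with it at 30. Grid results at 60 per arm, bound 3 vs bound 30:

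| Between-subject SD | Observed -1.5 kg: Pr(< -1 kg) | Observed -1.0 kg: Pr(< -2 kg) |
|---|---|---|
| 3.5 kg | 82.0% vs 78.1% | 3.3% vs 6.1% |
| 4 kg | 81.9% vs 75.2% | 3.4% vs 8.7% |
| 5 kg | 81.8% vs 70.7% | 3.5% vs 13.8% |

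At 30 per arm with an observed -1.5 kg, Pr(< -1 kg) is 74.3% vs 70.8%, 74.1% vs 68.4% and 74.0% vs 64.9%. When the observed difference equals the threshold, the probability is 50% under either bound.

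**The case against.** The strongest reply is that no harm is demonstrated. The documents give no weight SD, and nothing in them makes 3.5 kg more likely than 2.5 kg, where the bound does nothing. Even at 3.5 kg the probabilities in the examples move by only about 3 to 4 percentage points. Weight has no probability cut-off at the interim, the trial cannot stop there for efficacy, and the ITP weight model is labelled supportive. MMRM compares each investigational dose with 1.5 mg without any ceiling and is reported at the interim too, so a conspicuously small posterior SD could be noticed beside it. SAP 6.16.2.2 names no model for the interim weight probabilities. The word *similar* in 6.11.3.3 leaves a programmer a little room, and SAP 6.1 allows further analyses after datalock. The calculation is also idealised.

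Most of this stands as a limit on importance. The effect is conditional, the link to the interim is inferred from the matching thresholds, and the shift in the probabilities is modest at 3.5 kg and clearer from 4 kg. It does not remove the point. The sentence in 6.11.3.3 confines the change to theta and alpha, so the bound carries over as written. MMRM is a cross-check, but the protocol prefers Bayesian methods for this comparison. A prior changed after unblinded interim results have been seen would be open to the charge of being chosen post hoc.

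**Conclusion.** The concern holds. As written, both SDs in the body-weight ITP model are limited to 3 kg by a prior set for HbA1c in percentage points. The effect is nil up to a between-subject SD of about 2.5 kg and small at 3 kg. At 60 per arm the posterior SD of the difference is 15% too small at 3.5 kg, 26% at 4 kg and 40% at 5 kg; the interim figures at 30 per arm are similar. These sizes rest on assumed weight SDs, complete visits and data that follow the ITP model.

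Only the exploratory weight probabilities versus 1.5 mg are touched, together with their interim counterparts if the same model is used there. The primary HbA1c analysis, all MMRM analyses and the sample size are unaffected. This is an inexpensive improvement to make, not a shown error in a decision rule.

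**What to change.** In SAP 6.11.3.3, state the priors for the between- and within-subject SDs in kg with an upper bound that cannot bind, for example uniform(0.01, 30). Do this before the 120-completer interim, so that the prior is fixed before anyone sees unblinded weight results. In 6.16.2.2, a few words naming the model behind the interim weight probabilities would settle whether it applies there. A look at whether the SD posterior sits against its bound would also reveal the problem.

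The main cost is one line of SAP text and the matching line of code. If the weight SD proves to be 2.5 kg or less, the results do not change.

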6.12. Pharmacokinetic/Pharmacodynamic (PK/PD) Methods

All PK/PD analyses will be performed by Lilly and details will be documented in a separate analysis plan.

6.13. Safety Analyses

The safety analyses will include adverse events (AEs), serious adverse events (SAEs), AEs of special interest (AESIs), and treatment emergent adverse events (TEAEs), safety laboratory

analytes, vital signs, ECG. Adverse events of special interest include hypoglycemic and hyperglycemic episodes, pancreatitis, thyroid C-cell hyperplasia and C-cell neoplasms, allergic/hypersensitivity reactions, supraventricular arrhythmias and cardiac conduction disorders.

An AE will be coded using the Medical Dictionary for Regulatory Activities (MedDRA). TEAEs are defined as postbaseline events that are new events or preexisting conditions that worsened in severity after randomization using MedDRA low level term (LLT). The maximum severity level for baseline and post baseline for each same LLT term will be used as a criterion to determine TEAEs. If an AE occurs on the same date as the first dosing date with missing event occurring time, that event will be counted as post baseline event.

Unless otherwise specified, the ITT population will be used for analyses of safety measures, and all randomized population for data listing.

6.13.1. Extent of Exposure

Treatment exposure is defined as the time from when the patient took his/her first dose until the last dosing date. If that first dosing date is missing, it will be imputed with the date of randomization. If the last dosing date is missing, it will be imputed with the date the patient discontinued treatment or completed the treatment period, whichever is earlier.

Exposure will be calculated for each patient. It will be summarized for ITT population by treatment with mean, SD, minimum, maximum, the first quartile and the third quartile. The mean exposure duration in days among treatment groups will be compared with ANOVA model using treatment as a fixed effect. The p-value to compare the overall randomized treatment effect will be presented. The total patient-years of study drug exposure will be added at the end of the summary. Duration of exposure was categorized into the following groups: ≤ 28 days, > 28 to ≤ 42 days, > 42 to ≤ 56 days, > 56 to ≤ 70 days, > 70 to ≤ 98 days, > 98 and 126 days, > 126 days. These categories were summarized as frequency by treatment.

Similar summary reports will be generated separately for PP ad CS population. Each subject's detailed dose information at each post dose week (first dosing week will be coded as week 1) will be calculated based on the CRF sourced from the study drug administration log. For the maintenance phase, the dose information will use the package information for the missed injection(s). For the titration phase, the package information is not needed. For the first four weeks, missed injection means the entire dose is missed. For each of the last 2 titration week doses, missed 0, 1, and 2 injections means full dose, half dose, or no dose injected, respectively. This dose information along with the actual dosing date/time will be used for patient narratives, and PK analysis. The actual dosing information calculated in this section will be summarized by randomized treatment group. The exposure data will be listed for ITT population.

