**Table GBGJ.2. Study Treatments**

Treatment Arm	Titration Phase Dose a					Maintenance Phase Dose b
	Titration Algorithm	Total dose/ Administered as	6-week Titration Phase			12-week Dosing
			Week 0 and Week 1	Week 2 and Week 3	Week 4 and Week 5	Week 6 through Week 17
4.5 mg Dulaglutide	1	Total dose	1.5 mg QW	1.5 mg QW	3.0 mg QW	4.5 mg QW
		Administered as	1 × 1.5 mg PFS	1 × 1.5 mg PFS	2 × 1.5 mg PFS	3 × 1.5 mg PFS
	2	Total dose	0.75 mg QW	1.5 mg QW	1.5 mg QW	4.5 mg QW
		Administered as	1 × 0.75 mg PFS	1 × 1.5 mg PFS	2 × 0.75 mg PFS	3 × 1.5 mg PFS
3.0 mg Dulaglutide	1	Total dose	1.5 mg QW	1.5 mg QW	3.0 mg QW	3.0 mg QW
		Administered as	1 × 1.5 mg PFS	1 × 1.5 mg PFS	2 × 1.5 mg PFS	2 × 1.5 mg PFS + 1 × Placebo PFS
	2	Total dose	0.75 mg QW	1.5 mg QW	1.5 mg QW	3.0 mg QW
		Administered as	1 × 0.75 mg PFS	1 × 1.5 mg PFS	2 × 0.75 mg PFS	2 × 1.5 mg PFS + 1 × Placebo PFS
1.5 mg Dulaglutide	—	Total dose	1.5 mg QW	1.5 mg QW	1.5 mg QW	1.5 mg QW
		Administered as	1 × 1.5 mg PFS	1 × 1.5 mg PFS	2 × 0.75 mg PFS	1 × 1.5 mg PFS + 2 × Placebo PFS
Placebo	—	Total dose	Placebo	Placebo	Placebo	Placebo
		Administered as	1 × Placebo PFS	1 × Placebo PFS	2 × Placebo PFS	3 × Placebo PFS

Abbreviations: PFS = prefilled syringe; QW = once weekly.

- a Patients will administer 1 injection per week at the assigned dose for the first 4 weeks of the titration phase (Weeks 0, 1, 2, and 3), and 2 injections per week for the final 2 weeks of the titration phase (Weeks 4 and 5), totaling the assigned dose.
- b During the maintenance phase, patients (Weeks 6 through 17) will administer 3 injections per week (different combinations of dulaglutide and placebo totaling the assigned dose).

The investigator or his/her designee is responsible for the following:

- explaining the correct use of the study drug to the patient or patient representative
- explaining the correct use of metformin to the patient, including any contraindications and appropriate dosing per country-specific labeling
- verifying that treatment instructions described above are followed properly
- maintaining accurate records of study drug dispensing and collection

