### **7.2.1. Selection and Timing of Doses**

Patients will be allocated to 1 of the 3 dulaglutide doses (4.5 mg, 3.0 mg, or 1.5 mg) or placebo, each administered once weekly as subcutaneous injection(s). Rationale for the choice of the 2 investigational doses (4.5 mg and 3.0 mg) is provided in Section [5.5](#). The dulaglutide 1.5 mg dose was chosen as the active comparator since this is the highest dose approved by regulatory agencies. The randomization strategy is described in Section [7.2](#).

During the titration phase (end of Visit 3 to Visit 6 [Weeks 0 to 5]), patients assigned to investigational-dose dulaglutide (3.0 mg or 4.5 mg) will begin treatment using Algorithm 1 or Algorithm 2 (Table GBGJ.2). Patients assigned to dulaglutide 1.5 mg or placebo will begin administering treatment as assigned at Visit 3, without titration. During the maintenance phase (end of Visit 6 to Visit 12 [Weeks 6 to 17]), all patients will administer study drug at their final assigned dose. The assigned doses during the titration and maintenance periods may not be dextitratid. Patients with poor tolerability of the study treatments will be allowed to discontinue dosing temporarily (Section 8.1.2). Patients who discontinue study treatment temporarily and are then unable to tolerate it upon rechallenge will be discontinued from study drug and will be initiated on glycemic rescue therapy (Section 8.1.1).

It is recommended that patients inject the study drug at approximately the same time of day on the same day each week. For doses requiring multiple injections, the entire dose (all injections for that week) should be administered on the same day, within 30 minutes. The day and time of all dose administrations are to be recorded in diaries by the patients. If 1 or more injections are not given on the scheduled day, the missed injection(s) should be given as soon as possible after the scheduled day if there are at least 3 days (72 hours) until the next dose. If fewer than 3 days remain before the next scheduled dose, the missed injection(s) should be skipped and the next dose given at the regularly scheduled day and time.

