5.1. Summary of Study Design

Study H9X-MC-GBGJ (GBGJ) is a randomized, multicenter, placebo-controlled, double-blind Phase 2 trial in T2D patients on metformin monotherapy. The study is designed to assess the efficacy and safety of once weekly dulaglutide 3.0 mg and 4.5 mg in comparison to placebo. In addition, the trial will explore how these dulaglutide doses compare to the approved dulaglutide 1.5 mg dose to support dose selection for further development in Phase 3 trials, and to guide design of these additional trials. Study GBGJ will also explore the effect of 2 dulaglutide dose titration algorithms on gastrointestinal (GI) tolerability with investigational doses to guide design of the definitive algorithm to be evaluated in Phase 3 trials. The primary objective of this trial is to show superiority of the 3 dulaglutide doses (4.5 mg, 3.0 mg, 1.5 mg) to placebo in change in hemoglobin A1c (HbA1c) at 18 weeks.

During the trial, an unblinded internal assessment committee (AC) will review data on safety and tolerability in study participants according to a prespecified schedule in order to assure the safety of randomized patients. An efficacy/safety interim analysis will be conducted after approximately 120 patients have completed the 18-week therapy.

The study will consist of 3 periods: an approximately 2-week lead-in period, followed by an 18-week treatment period, and a 4-week safety follow-up period.

Figure [GBGJ.1](#) illustrates the study design.

[figure not shown]

Figure GBGJ.1. Illustration of study design for Clinical Protocol H9X-MC-GBGJ.

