6.9. Treatment Compliance

Treatment compliance in GBGJ is defined as taking at least 75% of the required injections for the prespecified time intervals: titration phase from the first dose to the sixth dose, and every 4 weeks thereafter: from the seventh dose to the 10th dose, from the 11th dose to the 14th dose, from the 15th dose to the 18th dose. Overall compliance is defined as being at least 75% compliant with investigational product across the treatment period. Compliance source data is from the site reported case report form (CRF) data.

Compliance will be summarized using ITT population by each randomized treatment and time interval, and overall. Listings will also be produced from all randomized population.

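### SAP 6.13.1 ends exposure at the last weekly injection but imputes a missing last date to the end of treatment, so identically treated patients can differ by about 7 days and patient-years come out roughly 5% to 7% low.

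*SAP*

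**What the plan says.** SAP 6.13.1 gives the definition: "Treatment exposure is defined as the time from when the patient took his/her first dose until the last dosing date". It adds no dosing interval after the last injection and does not say whether the first day counts. It then gives a rule for incomplete records: "If the last dosing date is missing, it will be imputed with the date the patient discontinued treatment or completed the treatment period", taking the earlier of the two dates. The same section plans a comparison of mean exposure days between arms by ANOVA, a total of patient-years, and a frequency table of exposure categories that ends with "> 98 and 126 days, > 126 days".

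The schedule behind these rules is once-weekly dosing (Protocol 7.2.1). Protocol Table GBGJ.2 starts dosing at Week 0 and places the maintenance doses at "Week 6 through Week 17". SAP 6.9 numbers the doses, with the final compliance interval running "from the 15th dose to the 18th dose". SAP 5.1 describes a lead-in "followed by an 18-week treatment period, and a 4-week safety follow-up period".

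**The concern.** The definition and the missing-date rule use different end points. With a recorded date, exposure stops on the day of the last injection. With a missing date, it runs to the end of treatment, which for a completer is about a week later. A recording gap therefore changes a patient's exposure when the treatment received is the same.

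The definition also does not match the scale of the category table. The cut-points 28, 42, 56, 70, 98 and 126 days are 7 times Weeks 4, 6, 8, 10, 14 and 18, so they count completed treatment weeks. The recorded-date rule counts one week fewer than the number of doses. At the lower extreme, a patient who qualifies for the ITT population with a single dose contributes 0 days (or 1) to the exposure table.

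At stake are the exposure summary, its patient-years total, and anything later built on that total. In proportion, the loss is largest for patients who stop early.

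**Working it through.** **Inputs.** Dosing interval 7 days (Protocol 7.2.1). Eighteen doses at Weeks 0 to 17 (SAP 6.9, Protocol Table GBGJ.2). Treatment period 18 weeks (SAP 5.1). About 300 randomized and 20% dropout (SAP 5.2). The documents do not give the timing of dropout or the share of missing last dosing dates, so both are treated as assumptions. Dropouts are taken to stop study drug when they drop out.

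**The plan's own figure.** 18 × 7 = 126 days. This reproduces the last cut-point and agrees with Visit 12 on day 127 in SAP Appendix 1 (126 + 1, with the first dose on day 1).

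**One patient.** After k on-schedule weekly doses with a recorded last date:

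- by the SAP rule: 7(k − 1) days
- counting the interval after the last dose: 7k days
- shortfall: 7 / 7k = 1/k

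| Doses taken | SAP rule (days) | With last interval (days) | Shortfall |
|---|---|---|---|
| 1 | 0 | 7 | 100% |
| 4 | 21 | 28 | 25% |
| 6 | 35 | 42 | 16.7% |
| 10 | 63 | 70 | 10% |
| 14 | 91 | 98 | 7.1% |
| 18 | 119 | 126 | 5.6% |

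If both end days count, a completer has 120 days and the shortfall is 6/126 = 4.8%.

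**Effect of a missing date.** A completer with a recorded last dose has 119 days. The same completer with that date missing is assigned the completion date, which is 126 days after the first dose if Visit 12 is on schedule. The difference is 7 days.

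**Trial total, all 300 completing.** 300 × 126 / 365.25 = 103.5 patient-years, against 300 × 119 / 365.25 = 97.7. The shortfall is 5.6%.

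**Trial total, 20% dropout.** Days with the last interval counted are 240 × 126 + 60 × 7k, where k is the mean number of doses among dropouts. With all last dates recorded, the loss is 300 × 7 = 2,100 days, or 300 × 6 = 1,800 if day 1 is counted.

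- All dropouts after 17 doses: 2,100 / 37,380 = 5.6% (1,800 / 37,380 = 4.8%).
- Dropouts spread evenly over doses 1 to 17 (mean 9): 2,100 / 34,020 = 6.2% (5.3%). In patient-years, 93.1 falls to 87.4.
- All dropouts after 1 dose: 2,100 / 30,660 = 6.9% (1,800 / 30,660 = 5.9%).

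**Trial total with some dates imputed.** If 10% of last dates are missing and those patients keep the full week, the evenly spread case becomes 1,890 / 34,020 = 5.6% and the all-completer case 1,890 / 37,800 = 5.0%.

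**Categories.** For on-schedule patients, the category changes only for those stopping after exactly 5, 7, 9, 11 or 15 doses. The 42-day cut marks the end of titration. By the SAP rule, 6 doses (titration only) give 35 days and 7 doses (first maintenance dose taken) give 42, and both fall in the band above 28 and up to 42. With the interval counted they are 42 and 49 and are separated. Counting both end days (36 and 43) also separates them, but the SAP does not state that convention.

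**The case against.** First-to-last-dose is an explicit convention. The documents nowhere say that exposure must cover the interval after an injection, and the SAP states no patient-years figure that could be miscalculated. Actual doses taken each week are derived and summarized separately in SAP 6.13.1, and compliance is counted by dose, so the last dose is not lost from reporting. This is a fair defense of the definition taken alone. It does not cover the missing-date rule, which uses a different end point in the same paragraph, or cut-points set at whole treatment weeks.

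A reader might infer several stronger points that the documents do not support.

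- **Every patient loses the final week.** Patients whose last dosing date is imputed can keep it.
- **The trial total is 5.6% low.** That is the figure for an on-schedule completer. The total depends on dropout timing and on imputed dates.
- **The category above 126 days shows the definition is wrong.** An imputed completion date can exceed 126 days because Visit 12 has a window of ±7 days. With the last interval counted, an on-schedule completer has exactly 126 days and is still not above the cut.
- **Planned safety rates are inflated, by 126/119 or about 5.9%.** No planned rate is stated to use this total. SAP 6.13.2 analyzes adverse events as proportions of patients, and the hypoglycemia model in SAP 6.13.4.1 uses log days between visits as its offset. The inflation would apply only to a rate later built on this total.
- **The total feeds the annual safety report.** SAP 6.18 lists cumulative exposure but does not say that it comes from this derivation.

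The ANOVA of mean exposure is also largely protected, because a constant 7-day shift cancels between arms. It does not cancel fully if the share of imputed dates differs by arm.

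**Conclusion.** The point holds as a minor inconsistency. SAP 6.13.1 credits an on-schedule completer with 119 or about 126 days according to whether the last dosing date was recorded, and its recorded-date rule does not fit its own category scale. Measured against 7 days per dose, patient-years are low by about 5.6% to 6.9% under the planned 20% dropout, or 4.8% to 5.9% if day 1 is counted. Imputed dates reduce the shortfall.

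These sizes assume on-schedule dosing, dropouts who stop drug when they drop out, and a weekly injection taken as 7 days of exposure. That last assumption is implied by the cut-points and the 18-week treatment period but is not stated in the SAP. No efficacy analysis, adverse event proportion or hypoglycemia rate changes.

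**What to change.** In SAP 6.13.1, define exposure as last recorded dose date minus first dose date plus 7 days, truncated at death or last contact. When the last dosing date is missing, use the discontinuation or completion date as the end of exposure and do not add 7 days; adding them would give a completer about 126 + 7 = 133 days. State that this day count applies to the category cut-points.

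An on-schedule completer then has 126 days with or without a recorded last date, and a one-dose patient normally has 7. For a discontinuer with a missing date, a difference of some days can remain, because the stop date need not fall exactly 7 days after the last injection.

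The cost is one line of SAP text and derivation code. Data collection does not change.
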